7.5 Post-intervention Follow-up Period

All participants will receive a follow-up phone call from the site investigator or designee 30 days \pm 7 days after Day 28 study visit to assess for any further AE and document resolution of any acquired AE during treatment. If the AE has not resolved, then the participant will be scheduled for a follow up visit with their primary care provider for ongoing management of this AE. The use of concomitant medications will be recorded.

7.6 Methods for Clinical Procedures

Breast core biopsy (see also section 10):

The breast core biopsy (image guided) will not be performed prior to drug initiation in the dose escalation cohort, and is optional at Day 28. The breast core biopsy (image guided) is required of participants in the dose expansion group at Day 28. A 14-gauge needle will be used. Every effort will be made to collect 4 cores of tissue, with the minimum of 3 cores per participant. Refer to Section 10 for details of specimen management.

8. CRITERIA FOR EVALUATION AND ENDPOINT DEFINITION

8.1 Primary Endpoint: Toxicity and Safety

The primary objective of this study is to determine the safety and toxicity of topical 1% bexarotene gel application to the breasts of healthy women at high risk for breast cancer for duration of 4 weeks. Women with ADH, ALH, LCIS, breast cancer survivors (DCIS or invasive) \geq 5 years from their diagnosis, BRCA 1/2 mutation carriers, and women with elevated risk for breast cancer \geq 1.7% in 5 years or lifetime risk \geq 20% will be recruited. Three dose levels are considered (10mg every other day, 10mg daily, and 20mg daily). Dose Limiting Toxicity (DLT) is defined as a grade 2 skin adverse event that persists for at least 6 days or any grade 3 or greater adverse event possibly, probably, or definitely related to the study drug. In addition, a DLT will be a grade 2 skin adverse event that recurs and persists for at least 3 days. A conservative modification of the standard “3+3” design will be applied. The first cohort of 3 participants will be treated at the first dose level (10mg every other day). New cohorts of participants will not be treated until toxicity has been fully evaluated for all current participants for 4 weeks. We will add another 4 participants when only 1 or less participants experience DLT in 6 treated participants. We will only escalate dose to the next higher level when 20% or less of total participants experience a DLT. At any dose level, the algorithm is as follows:

- (1) If 0 or 1 out of 3 participants experience DLTs (\leq 1/3), an additional cohort of 3 participants will be treated at the same dose level. If total number of participants experiencing DLT at that dose level is 1 or less out of 6 (\leq 1/6), we will enroll another 4 at the same dose level.
- (2) If at any time 2 or more participants experience DLTs in 3 or 6 (\geq 2/3 or \geq 2/6) or 3 or more experience DLT in 10 participants (\geq 3/10), then the dose escalation will stop, and the next lower dose will be considered as the maximum tolerated dose (MTD).
- (3) In 10 participants at each dose level, if we observe 2 or less DLTs, a cohort of 3 will be treated at the next higher level. If 3 or more in 10 participants experience DLT, we will stop accrual to that level and above, and claim the regimen as to be too toxic for that level or above.

MTD is defined the highest dose level with at most 2 participants with DLTs in 10 participants treated.

Once MTD is identified, we will enroll another 10 participants into MTD and these participants will have mandatory biopsies before and after 4 weeks of treatment. We will continuously monitor aggregate DLTs in these participants together with the 10 participants treated during the dose escalation part of the study. If at any time the posterior probability of observing a DLT rate of at least 20% exceeds 70%, i.e., $\Pr(\text{DLT rate} \geq 0.20 | \text{Data}) > 70\%$, given the prior of the DLT rate of beta (0.2, 0.8), we will stop the trial and claim the dose is too toxic. Given the above rule, the boundaries for early stopping due to excessive DLT are Total Number of Participants with DLTs/Total Number of Participants $\geq 4/11\sim 14$, $5/15\sim 19$, and $6/20$. Combining with the boundaries during dose escalation phase, i.e., stop accrual at the dose level if Total Number of Participants with DLTs/Total Number of Participants $\geq 2/3$, $2/6$, $3/10$, $4/11\sim 14$, $5/15\sim 19$, and $6/20$, the early stopping probability for this level will be 15%, 51%, 82% if the true DLT rate is 0.10, 0.20, and 0.30, respectively.

Given that there are 3 dose levels and 10 participants enrolled at each level, and 10 additional participants at MTD, it is anticipated that 40 participants will be enrolled and treated and up to 40 will be evaluable at the end of this study.

Skin Toxicity

CTCAE criteria will be utilized to grade adverse events. Skin adverse events are expected to be the most common in this study. Bexarotene is similar to retinoids and retinoid dermatitis is very common and can be managed with temporarily withholding drug and restarting at a decreased frequency until tolerated by the individual. Dose modifications for each dose level have been defined in Section 5.5 to guide management of participant experiences of an adverse event

CTCAE criteria for skin will be modified (Table 3) for this study as adverse events are expected to be localized to the breast area. This modified criteria was also utilized by Talpur *et al.* when they evaluated bexarotene 1% gel on the scalp of participants with alopecia areata (6). Please see Table 3 for modified CTCAE criteria. Use plain language when talking to the participant about skin AEs. Refer to Appendix G for a plain language guide to support both phone and in-person assessments of skin application AEs.

Participants will be shown how much area of their breast is considered 25% of the treated area so they can clearly describe their symptoms and the extent of the affected area. They will also be instructed to draw around reddened areas so they can clearly see if an area is expanding or improving and relay that information to the study team.

Table 3: Modified CTCAE for assessing skin toxicity of bexarotene gel applied to the breast skin. These assessments will be made on the breast skin (application site).

	Grade 1	Grade 2	Grade 3	Grade 4
Dry Skin	No erythema or pruritus	With erythema or pruritus	With erythema and pruritus	-
Pain of Skin	Mild pain	Moderate Pain	Severe Pain	-
Photosensitivity	Painless erythema	Mild to Moderate Pain with erythema	Erythema with blistering or skin breakdown	Erythema with ulceration
Pruritus	Mild, requiring topical intervention	Intense, with changes from	Intense, constant, limiting ADL or	-

		scratching, oral intervention needed	sleep, oral steroids needed	
Rash, maculopapular	Macules or papules <25% of treated area, with or without symptoms (pruritus, burning, tightness)	Macules or papules >25% of treated area, with or without symptoms (pruritus, burning, tightness), limiting instrumental ADL	Macules or papules >25% of the treated area, with or without symptoms (pruritus, burning, tightness), limiting self care ADL	-
Urticaria	Asymptomatic or mild symptoms, not requiring therapy	Moderate, limited local therapy needed, limiting instrumental ADL	Urticarial lesions covering >30% of application site; oral or IV intervention indicated	-

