Paresthesia	3 (6)	3 (6)
Respiratory		
Cough Increased	3 (6)	0
Pharyngitis	3 (6)	0

* Regardless of association with treatment

Includes Investigator terms such as:

¹ Contact dermatitis, irritant contact dermatitis, irritant dermatitis

² Pruritus, itching, itching of lesion

³ Erythema, scaling, irritation, redness, rash, dermatitis

⁴ Skin inflammation, excoriation, sticky or tacky sensation of skin; NOS = Not Otherwise Specified

Bexarotene 1% gel was also evaluated in a Phase I/II trial for alopecia areata and was applied to half of participants' scalp to assess response. Out of 42 patients, 31 (73%) experienced some dermal irritation with only 4 patients experiencing grade 3 dermal irritation. Most common adverse event noted was mild erythema in the area of treatment that resolved with discontinuation of the drug (6).

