11.1.3 Severity of AEs

11.1.3.1 Identify the AE using the CTCAE version 4.0. The CTCAE provides descriptive terminology (MedDRA lowest level term) and a grading scale for each AE listed. A copy of the CTCAE can be found at http://ctep.cancer.gov/protocolDevelopment/electronic_applications/ctc.htm

AEs will be assessed according to the grade associated with the CTCAE term. AEs that do not have a corresponding CTCAE term will be assessed according to the general guidelines for grading used in the CTCAE v4.0. as stated below.

CTCAE v4.0 general severity guidelines:

Grade	Severity	Description
1	Mild	Mild; asymptomatic or mild symptoms; clinical or diagnostic observations only; intervention not indicated.
2	Moderate	Moderate; minimal, local or noninvasive intervention indicated; limiting age-appropriate instrumental activities of daily living (ADL)*.
3	Severe	Severe or medically significant but not immediately life-threatening; hospitalization or prolongation of hospitalization indicated; disabling; limiting self-care ADL**.
4	Life-threatening	Life-threatening consequences; urgent intervention indicated.
5	Fatal	Death related to AE.

ADL

*Instrumental ADL refers to preparing meals, shopping for groceries or clothes, using the telephone, managing money, *etc.*

**Self-care ADL refers to bathing, dressing and undressing, feeding self, using the toilet, taking medications, and not bedridden.

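### Table 3 makes dry, red and itchy breast skin Grade 3 with no severity condition, so a mild related reaction can count as a dose-limiting toxicity

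*Combined protocol and SAP*

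**What the plan says.** Table 3 in Section 8.1 replaces the standard skin grading for this trial. Its Dry Skin row is graded by which signs accompany the dryness:

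- Grade 1: "No erythema or pruritus"
- Grade 2: "With erythema or pruritus"
- Grade 3: "With erythema and pruritus"

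On the Pruritus row, Grade 1 is "Mild, requiring topical intervention".

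Sections 8.1 and 13.4 count any Grade 3 or higher event judged at least possibly related as a DLT, with no minimum duration. A Grade 2 skin event must last at least 6 days, or recur and last at least 3. Sections 5.5 and 8.3 take a participant with any Grade 3 event off study drug. Section 7.3, for the Day 15 visit, says that drug is held pending dermatology review. Section 8.1 says of the expected reaction that "retinoid dermatitis is very common and can be managed with temporarily withholding drug and restarting at a decreased frequency until tolerated by the individual". The general scale in Section 11.1.3 describes Grade 3 as "Severe or medically significant but not immediately life-threatening".

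**The concern.** The step from Grade 2 to Grade 3 on the Dry Skin row turns on one conjunction. A woman whose dryness, redness and itch are all mild meets the Grade 3 cell as written. The event is then a DLT on the first day if it is related, and the duration test that protects a Grade 2 skin event from becoming a DLT does not apply. The hold-and-restart scheme in Section 5.5, which covers Grade 2 skin events, is bypassed as well.

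DLT is the primary endpoint and the only basis for the maximum tolerated dose (MTD), and few events decide each step. Section 3 reports that the second level closed on two DLTs among the three participants who remained. Under the Section 8.1 algorithm, one DLT in three would have led to three more participants at that level. Grading that depends on row wording rather than severity can therefore change the path of the trial.

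**Working it through.** **1. One presentation, graded row by row.** Take skin that is mildly dry, red, painless and mildly itchy, with the itch treated topically.

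| Table 3 row | Grade | Why |
|---|---|---|
| Dry Skin | 3 | redness and itch both present; intensity is not asked |
| Pruritus | 1 | mild itch with topical treatment |
| Photosensitivity | 1 | only if the redness is coded as a light reaction |
| Pain, maculopapular rash, urticaria | none | signs absent |

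**2. Grade 3 cells compared.** Pain requires severe pain. Pruritus requires intense, constant itch that limits activity or sleep, or needs oral steroids. Rash requires more than 25% of the treated area and limited self-care. Urticaria requires more than 30% of the site, with oral or intravenous treatment. Photosensitivity requires blistering or skin breakdown. Only Dry Skin has no such condition.

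**3. The interview.** Appendix G asks a woman with dry skin whether it is red or itchy. A yes fits the Grade 2 cell and the Grade 3 cell equally. The guide is used at the Day 8 call, when nobody examines the skin.

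**4. The plan's own operating figures.** Inputs are the Section 8.1 boundaries: stop at 2/3, 2/6, 3/10, 4 at 11 to 14, 5 at 15 to 19, and 6/20. Let f(n,k) be the probability of k DLTs after n women without stopping. Then f(n,k) = (1−p)·f(n−1,k) + p·f(n−1,k−1), and the mass at or above a boundary is removed at each look. The total removed is 15.0%, 51.3% and 82.3% at p = 0.10, 0.20 and 0.30. The plan states 15%, 51% and 82%, so its figures reproduce.

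**5. Sensitivity of the design (illustration).** Assume a DLT rate of 10% from other causes, and that a fraction f of women have the mild triad, all graded on the Dry Skin row, independently of other DLTs. The DLT rate is then 1 − 0.90·(1−f).

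- f = 0.10: 1 − 0.90·0.90 = 0.19; stopping probability 47%, against 15%
- f = 0.20: 1 − 0.90·0.80 = 0.28; stopping probability 77%

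**6. Plausible f.** No document gives it. Table 2 in Section 6.2 reports application-site rash (a pooled term that includes erythema) in 28/50 = 56% and application-site pruritus in 9/50 = 18%. The overlap is 0% at least, 0.56 × 0.18 = 10% if independent, and 18% at most. Counting all of it assumes that every such woman is also dry and is graded on that row. The source is lymphoma patients treated for up to 98 weeks, up to four times daily.

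**7. What that would do to the expansion.** These are stopping probabilities if this row were the only source of DLTs:

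| Rate from this row | Section 8.1 aggregate boundaries, starting from the observed 0/10 | Section 3 rule (30% or more, from the third expansion participant) |
|---|---|---|
| 0% | 0% | 0% |
| 10% | 0.1% | 30% |
| 18% | 1.3% | 53% |

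The Section 3 column uses boundaries of 1 at n = 3, 2 at 4 to 6, and 3 at 7 to 10. That the two rules differ is a separate inconsistency.

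**8. Evidence on frequency.** Section 3 reports 0/10 DLTs at the first level (one-sided 95% upper bound 1 − 0.05^(1/10) = 25.9%). Section 6.2 reports Grade 3 dermal irritation in 4/42 = 9.5% (exact 95% interval 2.7% to 22.6%) in the alopecia areata trial that Section 8.1 says used these criteria.

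**The case against.** **The triad is not shown to be the common reaction.** A reader might infer that the commonest expected reaction is graded as a DLT. The documents do not support that. Section 6.2 says of the alopecia trial: "Most common adverse event noted was mild erythema in the area of treatment". Erythema alone does not reach Grade 3 on the Dry Skin row, and Table 2 has no dry-skin term. The triad is foreseeable; its frequency is unknown.

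**Erythema is not ungradable.** It has no row of its own, although women are told about marking their skin: "They will also be instructed to draw around reddened areas". Section 11.1.3 applies the general scale to events without a corresponding term. That fallback stands. By the same sentence, however, the general scale does not override the Dry Skin row, which has its own criteria.

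**The highest grade counts in effect.** All adverse events are recorded, and any related Grade 3 event is a DLT, so dry skin recorded beside pruritus would count at its own grade. This has force, but it confirms that the mild triad is a DLT. It also leaves open whether the assessor enters dry skin, pruritus or both.

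**Safeguards exist.** Skin events at the Day 15 and Day 28 visits are photographed, and Grade 3 skin events go to dermatology. Nothing says that either step can change the grade.

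**A strict threshold suits a conservative design in healthy women.** That could justify the row if it were intended. The plan does not say so, and the other rows point the other way. The Section 8.1 remark on withholding and restarting is compatible with stopping at Grade 3 only if expected dermatitis stays at Grade 2 or below, which this row does not ensure.

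**Conclusion.** The defect is in the text and needs no assumption: followed exactly, Table 3 gives Grade 3 to a reaction whose components are all mild, and the DLT definition makes it dose-limiting once it is judged related. Its size cannot be determined from the documents. The 30% and 53% in the Section 3 column are illustrations that rest on assumed overlap of rash and itch, universal dryness and data from a more intensive regimen. Under the Section 8.1 boundaries, with 0/10 already observed, the same inputs give 0.1% and 1.3%. The 0/10 and 4/42 results suggest that the usual reaction is not graded this way.

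A reader might also infer that the declared MTD is wrong. The documents do not support that, because they give neither the row nor the grade of the two second-level DLTs. What can be said is that dependence of the dose conclusion on this row cannot be excluded until those events are listed.

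**What to change.** 1. Reconcile the Dry Skin row with the Pruritus row, the Section 11.1.3 scale, the Section 8.1 text on dermatitis, the consequences of Grade 3 in Sections 5.5, 7.3 and 8.3, and the Appendix G prompt. State how a presentation that meets several rows is graded. Which clinical threshold applies is for the sponsor; none is proposed here.
2. For every skin DLT, including the two at the second level, list the Table 3 row and grade that qualified it.
3. Report the DLT count at each dose level with and without events that qualify on the Dry Skin row alone.

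The cost is an amendment to Table 3 and Appendix G, plus one listing and one extra line in the DLT table. Section 11.1.2 already requires the verbatim term, coded term and grade, so much of the listing can be built from existing data.

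There are two downsides. Two DLT counts will be shown. Any change in grading must also be applied consistently to the first 10 participants before they are pooled with the expansion group; their result of 0/10 should not be assumed to survive every possible regrading.

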8.2 Secondary Endpoints

8.2.1 Markers of Systemic Toxicity: Based on data from oral bexarotene in women at high risk for breast cancer, bexarotene alters lipid levels, thyroid function, and calcium levels. Therefore, serum biomarkers to be tested will be Total Cholesterol, triglycerides, LDL, HDL, TSH, free T4, free T3, and calcium. Evaluation and changes in these biomarkers will be done at baseline, 15, and Day 28 visits.

8.2.2 Bexarotene Concentration: Bexarotene concentration will be determined using LC-MS/MS (5500 or similar; AB SCIEX, Foster City, CA) according to methods developed and qualified at IIT Research Institute (IITRI) for the study.

8.2.3 Effect of Bexarotene on Tissue Markers:

- i. One of the four cores collected from the core biopsies from post treatment (all dose expansion cohort participants and optional for dose escalation group) will be formalin-fixed and paraffin embedded (FFPE) for future histological analysis. These cores will be stored for future use.
- ii. One of the four cores collected from the core biopsies post treatment will be placed in RNALater and utilized for future biomarker analysis such as gene expression of RNA biomarkers.

8.3 Off-Agent Criteria

Participants may stop taking study agent for the following reasons: completed the protocol-prescribed intervention, AE or SAE including a DLT, inadequate agent supply, noncompliance, concomitant medications, medical contraindication, or became pregnant. Participants experiencing Grade 3 or Grade 4 toxicities of any attribution will be taken off study drug. Participants will continue to be followed, if possible, for safety reasons and in order to collect endpoint data according to the schedule of events. Participants that receive agent but withdraw without initiating treatment will be replaced and will not be followed or evaluable for DLTs.

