2.3 Rationale

In preclinical mouse models that develop ER-negative breast cancers, bexarotene showed significant activity in delaying mammary tumor development. In p53-null mice, bexarotene was given at 10mg/kg and 100mg/kg by gastric gavage and a 75% reduction in mammary tumor development was found in virgin mice at the higher dose level (7). In mouse mammary tumor virus (MMTV)-ErbB2 transgenic mice, focal tumors develop at eight months. Similar to humans, (MMTV)-ErbB2 mice undergo a multistage process of mammary tumorigenesis that progresses from normal mammary tissue to hyperplasia, mammary intraepithelial neoplasia (MIN) and finally invasive cancer. Li and colleagues gave bexarotene at 100mg/kg by oral gavage for 2 to 4 months in MMTV-erbB2 transgenic mice starting at three months of age. They found that bexarotene prevented the development of premalignant mammary lesions such as hyperplasia and MIN that is similar to human ductal carcinoma in situ (8).

Based on these preclinical findings, oral bexarotene at 200mg/m² has been evaluated in women at high risk for breast cancer based on their genetic risk. Bexarotene was found to reduce cyclin D1 RNA expression in breast cells from postmenopausal women (9). A nonsignificant reduction in Ki-67 expression was also seen in these post-menopausal women. Significant systemic side effects such as hypertriglyceridemia, hypercholesterolemia, and hypothyroidism were also found and were reversible after discontinuation of the drug(9). These results demonstrated that bexarotene has a biological effect on breast cells in women at high risk of breast cancer.

In addition to repressing cyclin D1 in breast cancer cells, bexarotene has shown effects on cyclin D1 in lung cancer cell lines. Dragnev et al. showed that the combination of bexarotene 1-4 μ mol/L plus erlotinib 1-4 μ mol/L significantly decreased cyclin D1 expression in cyclin-E- and KRAS/p53-driven transgenic lung cancer cell lines. The combination of bexarotene 400mg/m² per day plus erlotinib 150mg daily was evaluated in early stage non-small cell lung cancer patients in a window of opportunity trial and significant decreases in cyclin D1 were noted as well as an induction of necrosis and inflammatory responses (10).

Topical Therapies in Chemoprevention

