5.5 Dose Modification

For any grade 1 adverse events or grade 2 adverse events that are not hypertriglyceridemia or skin related, no dose modifications will be made. For any grade 2 skin toxicity possibly, probably, or definitely related to study drug that persists for 3 days, drug will be held for 3 days. Participants at the lowest dose level will restart gel application at every 3 days dosing for 3 days (1 dose) and then increase back to every other day dosing. If grade 2 skin toxicity recurs and persists for 3 days, drug application will be discontinued and will be classified as a DLT. Participants in the second dose level (10mg daily) will hold for 3 days if toxicity is noted and resume at 10mg every other day for 4 days (2 doses) and then increase back to daily dosing. Participants at the highest dose level (20mg daily) will hold for 3 days and resume at 10mg daily for 3 days (3 doses) and then increase back to 20mg daily. Participants experiencing Grade 3 or Grade 4 toxicities of any attribution will be taken off study drug. Please see Table 1 for dose modification algorithm.

Table 1: Dose Modification Algorithm for Grade 2 Skin Adverse Events related to Bexarotene Gel

Dose Level	If Grade 2 Skin AE Persists for 3 Days	Dose Modification (If Skin AE resolves to \leq Grade 1)	If Grade 2 Skin AE Recurs and Persists for 3 Days
10mg/breast/every other day	Hold Study Drug for 3 days	Restart drug application at 10mg/breast/every three days for 3 days (1 dose) and then increase to original dose	Stop Drug
10mg/breast/daily	Hold Study Drug for 3 days	Restart drug application at 10mg/breast/every other day for 4 days (2 doses) and then increase to original dose	Stop Drug
20mg/breast/daily	Hold Study Drug for 3 days	Restart drug at 10mg/breast/ daily for 3 days (3 doses) and then increase to original dose	Stop Drug

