Hypertriglyceridemia is a known systemic side effect with oral bexarotene formulation and will be monitored throughout the study. If grade 1 hypertriglyceridemia is noted, lipid profile will be continued to monitor weekly and at Day 22 blood specimen will be added for monitoring. If grade 2 hypertriglyceridemia is noted, drug will be held for 1 week and triglycerides will be rechecked. If normal, drug application will be resumed at the 1 dose level below. If triglycerides continue to be elevated or increase again, drug will be discontinued. If grade 3 hypertriglyceridemia is noted, drug will be discontinued and participant will be initiated on a statin. Triglycerides will be checked weekly until resolution and if elevation persists after 30 days, participant will be referred to their primary care physician for further management.

[figure not shown]

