13.5 Secondary Objectives, Endpoints, Analysis Plans

Secondary Objectives:

1. To detect bexarotene concentration in the serum at baseline and at 4 weeks of treatment.
2. To detect bexarotene concentration in the breast tissue at 4 weeks of treatment in the dose escalation group.
3. To investigate the effects of topical bexarotene on serum biomarkers
We will determine the change from the baseline in:
 - i. Lipid Biomarkers (Total Cholesterol, triglycerides, LDL, HDL)
 - ii. Thyroid Function Biomarkers (Thyroid Stimulating Hormone (TSH), T4, T3)
 - iii. Calcium

These measurements will be summarized using mean, standard deviation and median (range) for continuous variables at each time point. Wilcoxon rank-sum test may be used to examine the difference of continuous variables between participants' characteristics groups. Participants' demographic characteristics will be compared between different dose levels by Wilcoxon rank-sum and Fisher's exact test for continuous and categorical variables, respectively. In order to explore the changes over time, values of bexarotene concentration and biomarkers in serum will be plotted as functions of time (baseline, week 1, week 2, and week 4). Linear mixed effect model will be applied to model the biomarker change over time for all participants. Appropriate transformation and regression model will be used to ensure the model fit. Estimated bexarotene concentration mean in the breast tissue at 4 weeks will be calculated along with a 95% confidence interval. Other statistical methods may be applied when appropriate.

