13.8 Evaluation of Response

All participants included in the study must be assessed for response to intervention, even if there are major protocol deviations or if they are ineligible.

All of the participants who met the eligibility criteria (with the possible exception of those who did not receive study agent) will be included in the main analysis. All conclusions regarding secondary efficacy measures requiring breast biopsies will be based on eligible participants selecting this option.

Subanalyses may be performed on the subsets of participants, excluding those for whom major protocol deviations have been identified (e.g., early death due to other reasons, early discontinuation of intervention, major protocol violations, etc.). However, subanalyses may not serve as the basis for drawing conclusions concerning efficacy, and the reasons for excluding participants from the analysis should be clearly reported. For all measurements of response, the 95% confidence intervals should also be provided.

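### Day 28 tissue and serum samples from women already off the gel can be pooled into the 4-week concentration estimate, because no exposure condition is set

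*Combined protocol and SAP*

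**What the plan says.** **Who is sampled.** Under Section 5.5, gel stops early for severe toxicity ("Participants experiencing Grade 3 or Grade 4 toxicities of any attribution will be taken off study drug") and for recurrent skin toxicity ("If grade 2 skin toxicity recurs and persists for 3 days, drug application will be discontinued and will be classified as a DLT"). Grade 2 hypertriglyceridemia leads to a one-week hold, then discontinuation if triglycerides stay high or rise again. For grade 3, "If grade 3 hypertriglyceridemia is noted, drug will be discontinued and participant will be initiated on a statin". Section 8.3 nevertheless keeps these women on the schedule: "Participants will continue to be followed, if possible, for safety reasons and in order to collect endpoint data according to the schedule of events". At Day 28 the schedule (Sections 7.1 and 7.4) has research blood for bexarotene, routine labs and a core biopsy, which is mandatory in the expansion group.

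**What is estimated.** Section 13.5: "Estimated bexarotene concentration mean in the breast tissue at 4 weeks will be calculated along with a 95% confidence interval". Serum values are summarised by time point. For the markers, "Linear mixed effect model will be applied to model the biomarker change over time for all participants".

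**Who is analysed.** Section 13.8 puts eligible participants in the main analysis, with a possible exception only for those who received no agent. Conclusions from biopsy measures rest on the eligible women biopsied. Analyses leaving out early discontinuation are allowed, but "subanalyses may not serve as the basis for drawing conclusions concerning efficacy".

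**What is wanted.** Objective 1.1B concerns tissue concentration from 4 weeks at the MTD. Objective 1.2 asks for serum and tissue concentration at 4 weeks of treatment. A footnote to Section 7.1 has participants apply their last dose on Day 28.

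**The concern.** The objectives and the last-dose footnote describe an on-drug sample. The analysis text describes a calendar sample. The two agree only if every sampled woman is still on gel.

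A woman who stops at, say, Day 12 and is biopsied at Day 28 gives tissue 16 days after her last application. Her value enters the mean with the same weight as one taken during regular use. It measures what remains after stopping, which is not the quantity in Objective 1.1B, and it pulls the mean down.

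Nothing else in the plan separates such samples. The 75% compliance definition in Section 5.6 is tied to no analysis set. Section 13.6 deals only with missing data. Section 13.5 mentions neither time since last application nor statin start.

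At stake is the main product of the expansion group, a tissue concentration at the MTD from at most 10 biopsies, where one or two off-gel values carry visible weight. The lipid and thyroid markers face a milder form of the same problem. Section 2.3 reports that the effects of the oral drug "were also found and were reversible after discontinuation of the drug", so a Day 28 value taken after a stop may reflect recovery, and a lipid value after a statin may reflect the statin.

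**Working it through.** **1. The plan's own figures.** The plan gives no SD, precision target or washout rate for concentration. Its only related calculation is the DLT monitoring in Section 13.4. With the Beta(0.2, 0.8) prior, the smallest r satisfying Pr(rate ≥ 0.20 | data) > 0.70 is 4 at n = 11–14, 5 at n = 15–19 and 6 at n = 20, as stated. An exact sequential binomial calculation with looks at 3, 6, 10 and 11–20 gives:

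| True DLT rate | Stated stopping probability | Recomputed |
|---|---|---|
| 0.10 | 15% | 14.97% |
| 0.20 | 51% | 51.31% |
| 0.30 | 82% | 82.27% |

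These reproduce and are not in dispute.

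**2. Effect of pooling on the tissue mean.** Inputs: n = 10 expansion women (Section 3); k = number off gel when biopsied; f = fraction of the on-gel level remaining. f is not in the documents, so a range is assumed.

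Pooled mean / on-gel mean = [(10 - k) + k·f] / 10 = 1 - (k/10)(1 - f)

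| k | f = 0 (full washout) | f = 0.25 | f = 0.50 |
|---|---|---|---|
| 0 | 1.00 | 1.00 | 1.00 |
| 1 | 0.90 | 0.925 | 0.95 |
| 2 | 0.80 | 0.85 | 0.90 |
| 3 | 0.70 | 0.775 | 0.85 |

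**3. Plausible values of k.** Section 3 reports 0 DLTs in 10 women at the dose declared as MTD. Here each DLT is taken to mean a woman off gel.

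- Upper 95% limit for the DLT rate: one-sided 1 - 0.05^(1/10) = 25.9%; two-sided 1 - 0.025^(1/10) = 30.8%. So k up to about 3 cannot be excluded.
- Predictive distribution for the next 10 women: the plan's prior updated with 0/10 is Beta(0.2, 10.8), giving 87% for no DLT and 3.8% for two or more. A uniform prior gives 52% and 21%.
- At the planning rates 0.10, 0.20 and 0.30, ignoring the 0/10, the chance of at least one DLT is 1 - (1 - p)^10 = 65%, 89% and 97%. These are too pessimistic once 0/10 is known.

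Non-DLT stops would add to k, but no rate is given for them.

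**4. Effect on the interval.** Assume full washout and a between-woman CV of 50% (not in the documents). In 200,000 simulated lognormal samples, the planned 95% interval covers the on-gel mean in about 92%, 90%, 83% and 71% of trials for k = 0, 1, 2 and 3. At CV 30% the figures are 94%, 95%, 89% and 74%; at CV 100% they are 87%, 82%, 75% and 66%.

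**5. Precision cost of an on-gel mean.** At CV 50%, half-width as a fraction of the mean = t(0.975, m - 1) × 0.5/√m for m women:

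- m = 10: 2.262 × 0.5/√10 = 0.36
- m = 8: 2.365 × 0.5/√8 = 0.42
- m = 7: 2.447 × 0.5/√7 = 0.46

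**The case against.** **The problem may not arise.** Follow-up after stopping is only where possible, and Section 8.4 lists AE/SAE and non-compliance among the reasons for going off study, so some early stoppers will have no Day 28 sample. Sections 3 and 15 place the expansion biopsy at end of treatment, which for an early stopper need not mean Day 28. With 0/10 DLTs at the MTD, k = 0 is the most likely count under either prior above. All of this stands. It limits the expected size, but does not supply the missing rule.

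**A systemic effect would not be hidden.** A reader might infer that diluted Day 28 markers could let a gel with real systemic toxicity look clean. The documents do not support that. Clinically significant lab changes are reported as AEs (Section 11). A related grade 3 event is a DLT (Section 8.1), and toxicities are tabulated by dose level with grade, attribution and dates (Section 13.7). Grade 1 hypertriglyceridemia adds lipid monitoring (Section 5.5), and Day 15 values stay in the mixed model. Only the summary of marker change can be blurred.

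**The Section 13.8 restriction is narrow.** It concerns efficacy conclusions, and serum levels and safety labs are not efficacy measures. This stands for serum and markers. For tissue the text is unclear, because the same section speaks of secondary efficacy measures that need a biopsy.

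**Pooling is legitimate, and on-gel selection has its own bias.** An all-participants mean is a valid treatment-policy summary, and an on-gel mean drops women selected on toxicity. For the markers this is decisive against making an on-treatment model the main analysis, since a woman who stops before Day 15 would have no post-baseline value. For concentration it is weaker, because the stated objective is the level during treatment. Section 13.5 also reports median and range, which would partly reveal near-zero values.

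**Conclusion.** The point holds for tissue and serum bexarotene concentration. Section 8.3 allows off-agent samples, Sections 13.5 and 13.8 pool them without an exposure condition, and the objectives call for an on-treatment level.

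The tissue mean is understated by a factor between 1.00 and, in the worst case considered, 0.70. The low end requires 3 of 10 women off gel, all biopsied, with no drug left. A reader might take a 25–30% understatement as the expected size, but it treats an upper confidence limit as the share of women with zero tissue drug. With half the drug remaining, three off-gel women give 0.85. With nobody stopping there is no effect, and the 0/10 makes that plausible.

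The size for serum cannot be derived. Section 6.1 describes topical plasma levels as generally low and sporadic, so there may be little to dilute. The statin route needs grade 3 hypertriglyceridemia and is probably rare: Section 2.2 reports no such systemic effects with topical use, although Table 2 lists hyperlipemia in 5 of 50 patients. The 2 DLTs at dose level 2 bear on the marker model, not on tissue concentration at the MTD.

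**What to change.** **Section 13.5, concentration.** Make the main tissue and serum bexarotene estimate the mean with 95% CI in women still applying gel at their scheduled interval when sampled. List values from women on hold or off agent separately, with days since last application. Report the all-participants mean as a sensitivity analysis.

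**Section 13.8.** State that the restriction on subanalyses does not apply to concentration measures.

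**Section 13.5, lipids, thyroid tests and calcium.** Keep the all-participants mixed model. Flag values taken after gel stop or statin start, and add an on-treatment sensitivity analysis.

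**Biopsy timing.** Sections 3 and 15 (end of treatment) and Sections 7.1 and 7.4 (Day 28) differ for a woman who stops early, and must be reconciled.

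**Cost.** The analysis changes are wording only: application dates are in the gel diary and statin dates on the concomitant medication form. The price is a smaller n for the main mean (half-width about 0.42 of the mean with 8 women against 0.36 with 10, at the assumed 50% CV) and an estimate that describes women who stay on the gel, which is why the all-participants figure should appear beside it.
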